Sample Size	20 patients that have enrolled into the intermittent arm
Disease sites/Conditions	Advanced urothelial carcinoma
Interventions	A phase II study conducted investigating the use of intermittent CPI therapy in cisplatin ineligible or treatment refractory patients with aUC who respond to therapy. Patients will be treated with CPI therapy for at least 20 weeks as per standard of care (SOC), at which time those with a tumor burden reduction of 10% or greater will suspend CPI therapy. Patients with a documented increase in ≥ 20% tumor burden (RECIST 1.1 PD) will re-initiate CPI. For those patients who continue to have response, they will remain off therapy.

ABBREVIATIONS

CCCC	Case Comprehensive Cancer Center
CRF	Case Report Form
DSTC	Data Safety and Toxicity Committee
FDA	Food and Drug Administration
ICF	Informed Consent Form
IRB	Institutional Review Board
PRMC	Protocol Review and Monitoring Committee
SOC	Standard of Care
CCF	Cleveland Clinic Foundation
UH	University Hospitals
aUC	Advanced urothelial carcinoma
CPI	Checkpoint inhibitor
OS	Overall survival
PFS	Progression free survival
TFI	Treatment Free Interval
ORR	Overall response rate

TABLE OF CONTENTS

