6.5 Duration of Follow Up

Patients will continue to be followed for at least 30 days after the last dose of trial drug or until new anti-cancer treatment is initiated, whichever is earlier.

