14.0 STATISTICAL CONSIDERATIONS

14.1 Sample Size Justification

In this phase II study, we will enroll at least 50 patients with advanced urothelial carcinoma who are refractory to first line therapy or who are cisplatin ineligible. Patients will be treated with CPI therapy for at least 20 weeks as per standard of care (SOC), at which time those with a tumor burden reduction of 10% or greater will suspend CPI therapy. If the number of patients with tumor burden reduction of $\geq 10\%$ after 20 weeks is less than 20 patients, we will continue enrollment up to a maximum of 75 patients until the target sample size of 20 complete or partial responders has been reached. If we are not able to enroll 20 patients to the intermittent arm, after enrolling 75 patients, then we will deem the trial not feasible.

14.2 Safety considerations:

The primary safety endpoint is progression at 24 weeks post CPI suspension. Based on Keynote 045, we expect approximately 40% of patients in this group to progress within one year,⁴⁵ we would consider a progression rate of 60% or more within the first 24 weeks of CPI suspension to be unacceptable. A higher than expected rate of rapid progression would indicate CPI suspension is not safe in this patient population. Accordingly, we have incorporated continuous safety monitoring stopping rules into our design to ensure patient safety (Table 1). Specifically, we will stop

Table 1: Bayesian safety monitoring stopping rules. E.g. if we observed 4 or more PD by week 24 out of the first 6 patients, the trial will stop early.

Total number of patients	Number of patients with PD at 24 weeks
6	4-6
7 – 8	5-8
9 – 10	6-10
11 – 12	7-12
13 – 14	8-14
15 – 17	9-17
18-19	10-19

the trial early and declare CPI suspension unsafe if there is strong evidence that CPI suspension results in higher than expected rates of progression at 24 weeks. We will use Bayesian safety monitoring and stop the trial early if $\text{Prob}(\text{PD}_{24 \text{ wk}} > 0.4 \mid \text{data}) > 0.85$. We use a beta (0.4, 0.6) prior for the true rate of progression at 24 weeks, which corresponds to a prior expected progression rate of 0.4. Table 1 shows the corresponding stopping boundaries. If a patient progressed or died of disease, or lost to follow-up before 12 weeks, then the patient will be considered failure. Table 2 summarizes the operating characteristics.

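### The failure definition in 14.2 omits death from another or undetermined cause and a switch of cancer therapy without documented progression, so the week-24 stopping rule is weaker unless these count as failures

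*Combined protocol and SAP*

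**What the plan says.** Section 14.2 sets the endpoint: "The primary safety endpoint is progression at 24 weeks post CPI suspension". The trial stops once the posterior probability that the 24-week rate exceeds 0.4 passes 0.85, with this prior: "We use a beta (0.4, 0.6) prior for the true rate of progression at 24 weeks". Table 1 turns this into boundaries for 6 to 19 patients; for instance, "if we observed 4 or more PD by week 24 out of the first 6 patients, the trial will stop early".

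Failure is defined once: "If a patient progressed or died of disease, or lost to follow-up before 12 weeks, then the patient will be considered failure". The 12-week limit may qualify only loss to follow-up or the whole list. Either way it does not match a 24-week endpoint.

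Other sections bear on the omitted cases without scoring them:
- 6.3 prohibits concurrent anti-cancer therapy but gives no outcome to a patient who starts it.
- 6.4 item 5 allows removal for a change in condition, with no requirement for progression.
- 6.5 requires follow-up for at least 30 days after the last dose "or until new anti-cancer treatment is initiated, whichever is earlier".
- 11.0 has off-therapy imaging every 12 weeks, with a 6-week visit only if clinically indicated. Footnote 9 adds imaging whenever progression is suspected.
- 14.3 gives no rule for such patients at week 36 either.

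**The concern.** The sentence already goes beyond progression. It adds disease death and treats an unknown outcome (early loss to follow-up) as failure. It is then inconsistent that a known death off therapy counts only if attributed to disease. Cause of death is a site judgement in an open-label, single-arm study, and no adjudication is described.

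Such patients can arise. Someone who declines between scans may die with no progression recorded. Someone moved to other therapy may have no later scan, because required follow-up can end there. Loss to follow-up from week 12 to week 24 is also unscored.

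The rule is applied continuously to at most 20 patients, so one unclassified patient can decide a look. If poor outcomes off therapy fall outside the definition, the rule is less able to stop when it should.

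**Working it through.** **Inputs.** From 14.2: prior Beta(0.4, 0.6), threshold 0.4, posterior cut-off 0.85, Table 1 boundaries. Maximum of 20 patients in the intermittent arm (synopsis, 3.2). The rate of omitted events is not in the documents; I assume 2, 5 and 10 percentage points.

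**Step 1: reproduce the plan.** With x failures in n patients, the posterior is Beta(0.4 + x, 0.6 + n − x), and the rule stops if 1 − F(0.4) > 0.85, where F is its distribution function. The smallest x meeting this agrees with Table 1 at every n from 6 to 19. An exact binomial recursion, with a look after each patient from 6 to 19, reproduces Table 2:

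| True rate | Pr(stop), Table 2 | Pr(stop), recomputed |
|---|---|---|
| 0.3 | 0.12 | 0.120 |
| 0.4 | 0.34 | 0.343 |
| 0.5 | 0.65 | 0.646 |
| 0.6 | 0.88 | 0.883 |

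The tables are sound; the gap is in what counts as an event.

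**Step 2: one patient at a look.** Posterior probability that the rate exceeds 0.4:

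| Observed | Non-event | Excluded | Failure |
|---|---|---|---|
| 6 patients: 3 PD, 1 unlisted event | 3/6: 0.668 | 3/5: 0.796 | 4/6: 0.893 |
| 19 patients: 9 PD, 1 unlisted event | 9/19: 0.731 | 9/18: 0.795 | 10/19: 0.859 |

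In both rows only scoring as failure passes 0.85. At every n from 6 to 19, a count one short of the boundary stays below 0.85 as a non-event and passes it as a failure. Exclusion is less uniform: at n = 7 with 4 PD, dropping the patient leaves 4/6 = 0.893, which stops.

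**Step 3: effect over the trial.** Assume 60% fail by week 24 from all causes (progression, any death, or switch), of which a points are uncounted. Scored as non-events, the observed rate is 0.60 − a. Excluded, it is (0.60 − a)/(1 − a).

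| a | All counted | Non-events | Excluded, 20 evaluable patients |
|---|---|---|---|
| 0.02 | 0.88 | rate 0.58: 0.85 | 0.58/0.98 = 0.592: 0.87 |
| 0.05 | 0.88 | rate 0.55: 0.78 | 0.55/0.95 = 0.579: 0.84 |
| 0.10 | 0.88 | rate 0.50: 0.65 | 0.50/0.90 = 0.556: 0.79 |

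If excluded patients are not replaced, so that 20 are enrolled rather than evaluable, the last column is 0.87, 0.84 and 0.77.

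**Step 4: cost of counting everything.** With true progression at 40%, adding 5 points of unrelated events gives a rate of 0.45 and raises Pr(stop) from 0.34 to 0.49. Adding 10 points gives 0.50 and 0.65.

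**The case against.** A progression-specific endpoint is defensible. The stated worry in 14.2 is rapid progression, and death from intercurrent illness is not plain evidence that suspension did harm. The protocol's benchmark is also a progression rate: "we would consider a progression rate of 60% or more within the first 24 weeks of CPI suspension to be unacceptable". At a true progression rate of 60% the stated 0.88 stands. The losses in step 3 appear only if 60% is taken as an all-cause rate, and that is my assumption.

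The gap is narrower than the 12-week schedule suggests. Footnote 9 in 11.0 calls for imaging on suspicion of progression, 6.3 prohibits other therapy on study, and 3.1 and 3.3 tie CPI re-start to progression. These make undocumented failures less likely, but do not say how to score one that occurs.

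Three stronger readings are tempting and not supported:
- That the plan scores these patients as non-events. It is silent, and exclusion fits the text as well, with a smaller effect.
- That the rule would show suspension to be safe. It can only declare suspension unsafe; not stopping is not a finding of safety.
- That Tables 1 and 2 are wrong. Both reproduce.

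What remains is that neither reading counts these patients as failures, and the text does not choose between them.

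**Conclusion.** The concern holds as an incomplete event definition in a safety stopping rule. Under an assumed all-cause failure rate of 60%, the loss in stopping probability is small at 2 uncounted points (0.03 as non-events, about 0.01 if excluded) and material at 10 points (0.23 and about 0.09). Because the documents give no rate for these events, the range is the finding and no single value should be quoted. The point about a single look needs no assumed rate: at 6 patients with 3 progressions, how one unlisted event is scored determines whether the trial stops. The definition should be settled before monitoring begins, since any later choice would be made with the patient's outcome known.

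**What to change.** In 14.2, define failure for Table 1 as RECIST progression, death from any cause (at minimum, death that is disease-related or of undetermined cause), start of other anti-cancer therapy or CPI re-start without documented progression, or loss to follow-up, all through the 24-week window. Reconcile the 12-week limit with the 24-week endpoint in the same edit; changing the event list alone would leave weeks 12 to 24 unclear. State that all suspended patients stay in the denominator. Score the week-36 outcome in 14.3 the same way over its own window, and report the progression-only rate and deaths by cause alongside.

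Relabel Table 2 by composite failure rate, and confirm that the 0.4 threshold, set for progression, is still intended. State the downside openly: more early stopping if unrelated events occur, as in step 4.

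The cost is a few sentences plus one data requirement. Sections 6.5 and 8.5 tie required follow-up and routine serious adverse event collection to 30 days after dosing or to the next treatment. A line requiring vital status and new-therapy status through weeks 24 and 36 would cover this. The change concerns endpoint scoring only and leaves clinical management untouched.

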3.2 Number of Subjects

Our goal is to enroll 20 CPI-eligible patients onto the intermittent arm. We will first screen up to 50 patients for this study in order to get our target sample size. If, there are not at least 20 patients with a tumor burden reduction of 10% or greater, we will continue to screen up to 25 more patients (total of 75 patients). If we screen 75 patients without enrolling 20 patients into the intermittent arm, we will stop the trial and deem it not feasible (refer to section 14.1 for sample size justification)

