Table 2. Summary of operating characteristics based on 10,000 simulations using monitoring rules specified in table 1. If the true PD rate at 24 weeks is 60%, the early stopping probability is 0.88.

Scenario	True PD rate at 24 weeks	Pr(Early Stoppng)	Average Sample Size	Average Number of PD Observed by Week 24
1	0.3	0.12	18.6	5.6
2	0.4	0.34	16.3	6.5
3	0.5	0.65	12.9	6.5
4	0.6	0.88	9.7	5.8

14.3 Efficacy:

Our primary efficacy endpoint is sustaining a response at 36 weeks following CPI suspension, and our primary objective is to estimate the proportion of patients able to sustain a response. We will estimate this proportion and construct an exact binomial 95% CI. With 20 patients, the half-width of the 95% CI won't exceed 0.23.

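### Table 2 gives stopping probabilities for progression alone, while section 14.2 also makes loss to follow-up before 12 weeks a failure; on the natural reading, early loss raises the chance of stopping above the stated figures

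*Combined protocol and SAP*

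**What the plan says.** Section 14.2 takes progression at 24 weeks after CPI suspension as the primary safety endpoint. It sets the unacceptable level in these words: "we would consider a progression rate of 60% or more within the first 24 weeks of CPI suspension to be unacceptable". The monitoring rule is to stop "the trial early and declare CPI suspension unsafe if there is strong evidence that CPI suspension results in higher than expected rates of progression", judged at week 24. In formal terms the trial stops if the posterior probability that the 24-week PD rate exceeds 0.4 is above 0.85. The prior is given as follows: "We use a beta (0.4, 0.6) prior for the true rate of progression at 24 weeks".

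Table 1 turns this into counts of patients with PD at 24 weeks. Its example reads: "if we observed 4 or more PD by week 24 out of the first 6 patients, the trial will stop early".

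Between the references to Table 1 and Table 2, section 14.2 adds: "If a patient progressed or died of disease, or lost to follow-up before 12 weeks, then the patient will be considered failure".

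Table 2 is captioned "Summary of operating characteristics based on 10,000 simulations using monitoring rules specified in table 1". Its rows are true PD rates of 0.3, 0.4, 0.5 and 0.6. Its results are the early-stopping probability, the average sample size and the average number of PDs observed by week 24. No loss rate appears in the table or elsewhere in section 14.

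**The concern.** The failure sentence adds an event, loss before week 12, that the simulation behind Table 2 does not appear to include. If lost patients enter the Table 1 count, the rule sees an event rate above the PD rate whenever some of them would otherwise have reached week 24 without progression. Table 2 then understates how often the trial stops at a given PD rate.

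This matters most at PD rates of 0.3 and 0.4. Those lie well below the level the plan calls unacceptable, and 0.4 is the mean of its prior. A stop there ends a 20-patient study and declares suspension unsafe. Table 2 is the plan's only statement of how often that would happen.

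The count and the criterion can also disagree. The criterion concerns the PD rate, yet a boundary could be crossed partly by patients whose progression status is unknown.

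**Working it through.** **Inputs.** Section 14.2 gives the prior Beta(0.4, 0.6), the threshold 0.4 and the cutoff 0.85. Table 1 stops the trial at 4 events of 6; 5 of 7–8; 6 of 9–10; 7 of 11–12; 8 of 13–14; 9 of 15–17; 10 of 18–19. Section 3.2 gives the maximum of 20 patients in the intermittent arm. The early-loss probability L is an assumption, because the documents give none.

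**Step 1: Table 1.** With x events in n patients the posterior is Beta(0.4 + x, 0.6 + n − x). The smallest x with Pr(rate > 0.4) > 0.85 matches Table 1 at every n from 6 to 19. For example, 4 of 6 gives 0.893 and 3 of 6 gives 0.668.

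**Step 2: Table 2 with PD as the only event.** I used an exact recursion: one event per patient with probability p, boundaries checked after each patient from n = 6 to 19, and a maximum of 20.

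| True PD rate p | Pr(stop), exact | Pr(stop), stated | Average N | Average PDs |
|---|---|---|---|---|
| 0.3 | 0.120 | 0.12 | 18.6 | 5.6 |
| 0.4 | 0.343 | 0.34 | 16.3 | 6.5 |
| 0.5 | 0.646 | 0.65 | 12.9 | 6.5 |
| 0.6 | 0.883 | 0.88 | 9.7 | 5.8 |

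All 12 entries match the plan to rounding. So Table 2 is arithmetically right, and it was computed with no loss component.

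**Step 3: early loss counted as failure, independent of PD.** The event probability becomes f = p + L(1 − p). For p = 0.4 and L = 0.05, f = 0.4 + 0.05 × 0.6 = 0.43. Running the same recursion at f gives Pr(stop):

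| L (assumed) | p = 0.3 | p = 0.4 | p = 0.5 | p = 0.6 |
|---|---|---|---|---|
| 0 (as stated) | 0.12 | 0.34 | 0.65 | 0.88 |
| 2% | 0.14 | 0.38 | 0.68 | 0.90 |
| 5% | 0.18 | 0.43 | 0.72 | 0.91 |
| 10% | 0.26 | 0.52 | 0.78 | 0.94 |

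At 10% loss the average sample size is 17.1/14.3/11.2/8.6, against 18.6/16.3/12.9/9.7 stated.

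**Step 4: loss related to progression.** Hold the PD rate at p and suppose that a share s of the lost patients would have progressed by week 24. Only the others add events, so f = p + L(1 − s). With L = 0.10 and s = 0.8, f = p + 0.02, and Pr(stop) is 0.15/0.40/0.70/0.91. With s = 1, f = p and Table 2 is unchanged.

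**Step 5: loss in weeks 12 to 24.** The plan does not say how such a patient is counted. Suppose the patient counts as non-PD, with a constant progression hazard over the two 12-week periods, so that h = 1 − √(1 − p) in each. With loss L₁ in the first period and L₂ in the second, f = L₁ + (1 − L₁)[h + (1 − h)(1 − L₂)h].

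- 5% in each period: 0.17/0.41/0.69/0.90, still above Table 2.
- No early loss and 5% late loss: 0.11/0.32/0.62/0.86, below Table 2.

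**Step 6: count against criterion.** Three PDs and one early loss among the first six make four failures, which reaches the boundary. The PD-only posterior is Beta(3.4, 2.6) if the lost patient is excluded, giving Pr(rate > 0.4) = 0.80. It is Beta(3.4, 3.6) if that patient is kept as non-PD, giving 0.67. Both are below 0.85.

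**The case against.** The strongest reply is that section 14.2 never says outright that failures enter the Table 1 count. The table's column, its example and the posterior all refer to PD, and section 14.4 analyses a success status to which the word failure could belong. If the failure sentence has no bearing on Table 1, Table 2 stands as printed. That possibility is real. But the sentence sits inside the stopping-rule paragraph, between the two tables, so the stopping count is its natural reading. Either way the text needs to say which is meant.

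It is also fair that counting early loss as failure is a cautious choice for a safety rule. Detection at the unacceptable 60% rate rises with it (0.88 to 0.91 at 5% loss); the cost is more stopping at lower PD rates. Nothing here argues for dropping that choice, only for reporting its consequences.

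The size rests on an assumed loss rate: in 20 patients, 5% is one patient and 10% is two. Independence is also debatable. Off-therapy imaging is every 12 weeks (sections 3.3 and 11.0), so a patient lost before week 12 may have no off-therapy scan, and loss may reflect decline. This part of the objection stands, and it is why a range is shown.

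A reader might infer three stronger things that the documents do not support. Table 2 is not miscalculated. Not every loss counts as a failure, because the sentence stops at 12 weeks. And stopping is not higher than stated in all circumstances: with only late loss, counted as non-PD, it would be lower.

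**Conclusion.** The point holds in a conditional form. Table 2 correctly describes a rule that counts progression alone. The rule as section 14.2 most naturally reads also counts loss before 12 weeks, and Table 2 does not describe that rule once any such loss falls on patients who would not have progressed by week 24.

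The direction follows from the failure definition, subject to the unspecified handling of later loss. The size depends on assumption. At a PD rate of 0.4 and 10% early loss, the stopping probability is 0.52 if loss is independent of PD, 0.40 if 80% of those lost would have progressed, and the stated 0.34 if all would have. Under independence the effect is mainly on false stopping: at 10% loss it roughly doubles at a PD rate of 0.3 (0.12 to 0.26), while the gain at 0.6 is about 6 points (0.88 to 0.94). About 1% early loss is enough to move the figure at 0.4 by 2 points (0.34 to 0.36).

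The possible conflict between a boundary reached partly through loss and the PD criterion needs no assumed loss rate, as the 3 PDs plus 1 loss of 6 shows. It does rest on failures entering the Table 1 count. This should be corrected, but it calls for no change to the boundaries or the sample size.

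**What to change.** 1. State in section 14.2 that the Table 1 count is failures as that section defines them: progression, death of disease, or loss to follow-up before 12 weeks. Relabel the Table 1 column and its example to match. If failures are not meant to enter the count, say so and state what the failure definition is for.
2. Reconcile the 12-week window with the 24-week endpoint, including how a patient lost between weeks 12 and 24 is counted.
3. Either index Table 2 by the true total failure rate, which leaves its stopping probabilities and average sample sizes as they are but means relabelling its PD columns as failures, or re-run it by true PD rate with stated early-loss rates, for example 0%, 2%, 5% and 10%, giving the assumption about how loss relates to PD.
4. If a boundary is reached with losses among the failures, report the PD-only posterior beside it as a descriptive figure. It should not alter the stopping rule.

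The work is a small simulation and a few lines of text. The real cost is that the stated false-stop probabilities at PD rates of 30–40% become less favourable.

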14.4 Analysis Plan

Summary statistics of toxicity and success status will be provided in frequencies and percentages. Toxicity and success rates will be estimated along with 95% CIs. Logistic regression model will be used to explore effects of patient and tumor characteristics on toxicity or success status. Survival endpoints will be estimated by Kaplan-Meier method and compared by log rank test. Cox proportional hazard model will be used to associate clinical factors and biomarkers with survival endpoints. Other statistical analyses will be carried out as appropriate.

